## 7.2 Study Rationale

The interaction between cancer cells and the tumor microenvironment is complex, but recent research has begun to reveal the mechanisms by which a successful tumor embeds itself within a network of supporting normal cells, such that targeting the tumor microenvironment is at the forefront of developments in novel cancer therapy (Hanahan and Weinberg 2011). The human immune system is empowered to fight foreign antigens by a continuous surveillance around the whole body. Though immune cells are able to impair early tumor development in most people, in cancers that reach clinical attention, the immune system has become immune tolerant of the tumor tissue at both local and systemic levels (Schreiber, et al., 2011).

An approach to effectively break immune tolerance in cancer subjects holds the key to successful cancer immune therapy. Recent Food and Drug Administration (FDA) approval of two cancer immune therapies that specifically target cancer-hijacked immune support systems, anti-CTLA4 (Yervoy®; ipilimumab) and dendritic cells modified ex vivo (Provenge®; sipuleucel T), exemplified this trend. Several additional therapies targeting the immune components of the tumor microenvironment (eg, nivolumab) are currently in clinical trials with very promising clinical effects (Brahmer, et al., 2012; Topalian, et al., 2012).

Immunosuppressive signals come from cancer cells as well as immune cells (Figure 2). CTLA4 blockade inhibits the suppressive signals from effector T cells (cytotoxic T cells and Th1/2 cells) themselves and from Treg cells, while PD1/PDL1 blockade mainly inhibits the signals from cancer cells (Brahmer, et al., 2012; Topalian, et al., 2012). Another immunosuppressive mechanism in the tumor microenvironment is supplied by myeloid cells. Myeloid cells respond to signals in their local environment by acquiring a phenotype that is appropriate for the condition. These phenotypes are considered either type 1 (M1Mφ), which are pro-inflammatory, antimicrobial and antitumor antigen-presenting macrophages, or type 2 (M2Mφ), which are pro-angiogenic, anti-inflammatory, immunosuppressive wound-healing MDSC and TAM.

The presence or accumulation of TAM and MDSC cells in tumors is well documented in the literature to be associated with a poorer prognosis in many types of human carcinomas and adenocarcinomas, including colon, pancreatic, lung, breast, head and neck squamous cell (HNSCC), prostate, hepatocellular carcinoma (HCC) and colorectal (CRC), thyroid, melanoma and others (Joyce and Pollard, 2009; Ganjoo, et al., 2011; Medrek, et al., 2012; Zhang, et al., 2012).

Due to its exquisite receptor selectivity, oral bioavailability, strong preclinical safety profile, and unique antitumor mechanism, E7046 is an excellent candidate to be developed as a novel anticancer immune therapy by targeting immunosuppressive TAM/MDSC. Treatment with E7046 is intended to modify the immunosuppressive tumor microenvironment by inhibiting the accumulation of MDSC and TAM, and thus permitting enhanced host immune responses against the tumor.

## 8 STUDY OBJECTIVES

### 8.1 Primary Objectives

The primary objective of the study is to:

- Assess the safety/tolerability profile of E7046 as a single agent administered orally once daily, continuously in 21-day cycles, in subjects with selected advanced and/or recurrent malignancies.
- Determine the MTD and/or RP2D of E7046.

### 8.2 Secondary Objectives

The secondary objectives of the study are to:

- Evaluate the pharmacokinetic (PK) profile of E7046.
- Evaluate the ORR according to immune-related RECIST (irRECIST) in subjects treated with E7046 with selected tumor types with high level of myeloid infiltrate
- Evaluate the following additional efficacy endpoints according to irRECIST: time to response (TTR), duration of response (DOR), progression-free survival (PFS), disease control rate (DCR), and clinical benefit rate (CBR).

### 8.3 Exploratory Objectives

The exploratory objectives of the study are to:

- Explore efficacy according to modified RECIST 1.1, using the following endpoints: ORR, TTR, DOR, PFS, DCR, and CBR
- Assess overall survival (OS)
- Explore the pharmacodynamic effect of E7046 on selected immune cell populations and selected biomarkers in tumor infiltrate and in peripheral blood.
- Explore FDG-PET as a biomarker of response
- Explore the pharmacokinetic/pharmacodynamic (PK/PD) relationship

## 9 INVESTIGATIONAL PLAN

### 9.1 Overall Study Design and Plan

This is an open label, multicenter, Phase 1 study that will be conducted in 2 parts: a dose escalation part and a cohort expansion part. The objective of the dose escalation part is to assess the safety and tolerability and determine the MTD and/or RP2D of E7046. In the cohort expansion part an additional 6 to 16 subjects will be treated at the RP2D to further characterize safety, efficacy, PK, and PD. E7046 is a novel cancer immune therapy and as this is the first study in humans therefore a cautious approach in the first cohort of subjects is prudent. Staggered start of dosing in the first cohort will thus be implemented to ensure exposure of a limited number of subjects in the initial dosing cohort.

The applicability of conventional *MTD finding* Phase 1 designs for compounds with minimum expected toxicity has been discussed in various publications, and several alternative strategies have been advised ([Rubinstein and Simon, 2003](#)). Pharmacokinetics based and minimal biologically active dose finding designs rely not only on having robust estimates from preclinical data but also the use of biological correlative response endpoints that might get complicated by issues of assay adequacy and access to biological tissues. Another strategy for Phase 1 studies of targeted compounds is to compare dose levels with regard to biological response in normal tissue using an optimized highly reproducible assay. If use of normal tissue for assessing biological response is not possible or if a highly reproducible assay is not available, characterisation of an optimal biologic dose may not be feasible or might require a large sample size.

The study design was selected taking these concerns into account. A major consideration was that the toxicities of E7046 are likely to be moderate in the dose range planned and an MTD may not be reached (according to preclinical results). It is anticipated that the RP2D will be selected based on integrated evaluation of safety, tolerability, clinical benefit, PK, and PD data, collected from all dose levels tested. Accordingly, a modification of the standard 3+3 design was selected, where dose cohorts of 6 subjects will be enrolled at each of the 4 dose levels to be tested so as to provide sufficient data for selecting RP2D in the absence of an MTD.

### 9.1.1 Dose Escalation

#### 9.1.1.1 Dose Escalation Design

E7046 will be tested in sequential escalating dose cohorts of 6 subjects per cohort, at the dose levels shown in [Table 1](#). Subjects will be assigned to a dose level in the order of study entry. Intermediate dose levels may be explored.

**Table 1 Dose Cohorts in E7046 Dose-Escalation**

Dose level	No. of Subjects	E7046 Dose
-1	6	75 mg QD
1	6	125 mg QD
2	6	250 mg QD
3	6	500 mg QD
4	6	750 mg QD

QD = once daily.

The schema for dose escalation is adopted and modified from the traditional 3+3 design and is shown in [Figure 3](#). Dose limiting toxicities are defined in [Section 9.1.1.2](#).

Enrollment for first dose cohort (125 mg QD): (see Figure 3 Panel B)

In the first cohort, staggered dosing will be employed as described below.

Suspected severe immune reactions (ssIR) are defined as listed in the CTCAE v4.03 "Immune System Disorders", including Allergic Reaction, Anaphylaxis, and Cytokine Release Syndrome.

*First 3 subjects (Subjects 1, 2, and 3)*

- Initially one subject (Subject #1) will be enrolled and dosed.
  - If after 14 days of dosing no suspected severe immune reactions are observed, another 2 subjects (Subjects # 2 and 3) will be enrolled and dosed.
  - If within the first 14 days, Subject #1 experiences a suspected severe immune reaction, another subject (Subject #2) will be enrolled and dosed.
    - If after 14 days of dosing no suspected severe immune reactions are observed for Subject #2, another subject (Subject #3) will be enrolled and dosed.
    - If within the first 14 days, Subject #2 also experiences a suspected severe immune reaction, enrollment in this dose cohort will stop. A lower dose level of 75 mg QD (Dose Level -1) may be tested. Enrollment of the 6 subjects at Dose Level -1 will follow the same staggered schema as described for Dose Level 1.

*Next 3 subjects (Subjects 4, 5, and 6)*

- After evaluation of the first 3 subjects for DLTs after 21 days (Cycle 1), enrollment will continue as follows:
  - If  $\leq 1$  of 3 first subjects experiences DLTs in Cycle 1, the remaining 3 subjects (Subjects # 4, 5, and 6) in the first cohort will be enrolled and treated.
  - If  $>1$  of 3 first subjects experiences DLTs in Cycle 1, a lower dose level of 75 mg (dose level -1) will be tested, following the same enrollment schema as described for Dose Level 1.

Enrollment of subsequent dose cohorts:

[figure not shown]
- There will be no staggered dosing after the first dose cohort, however the subject enrolment will be controlled so that no more than one subject will be dosed on the same day.
- If  $\geq 2$  of 6 subjects in any dose cohort experiences a DLT, then dose escalation will be stopped.
- If  $\leq 1$  of 6 subjects in a dose cohort experiences a DLT, then 6 subjects will be enrolled at the next higher dose level. Dose escalation will continue until a dose level is reached where  $\geq 2$  subjects experience a DLT, or when 750 mg is reached based on

an integrated evaluation of safety, tolerability, clinical benefit, PK, and pharmacodynamic data, for all dose levels tested.

[figure not shown]
Additional enrollment (if necessary)

If needed for selection of RP2D, an additional 3 subjects may be enrolled at 1 or 2 selected dose levels.

Panel A: Overall Dose Escalation Schema

Panel B: First Dose Cohort (Staggered dosing)

ssIR = suspected severe immune reaction

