#### 7.1.3.3 Toxicology and Safety Pharmacology

Toxicity of E7046 was evaluated in single- and repeated-dose oral toxicity studies in male and female rats and dogs (up to 4 weeks). E7046 induced similar toxicities across preclinical species. Major findings in dogs and rats were limited to dose-dependent intestinal effects and testicular toxicity. Intestinal changes were characterized by abnormal stools which resulted in progressive weight loss at highest dose tested. In addition, E7046 induced minor changes in heart rate and blood pressure (BP) in the dog at exposures more than 2 fold higher than the predicted efficacious human exposure.

The proposed starting dose in humans of 125 mg is less than 1/9 of the human dose equivalent in dogs that caused only occasional mucous stool and slight testicular changes. If translated into the clinic, both would be considered acceptable changes in the intended subject population. Based on the observed toxicities in preclinical species, E7046 may cause the side effects in humans including, but not limited to, the following:

**Gastrointestinal system:** Colitis, characterized by new onset of diarrhea, which may be accompanied by abdominal pain and or gastrointestinal bleeding.

**Testicular system:** Decreased testicular weight, hypo cellularity.

**Cardiovascular system:** Reversible increase in heart rate and decrease in mean blood pressure.

Safety pharmacology of E7046 was evaluated in vitro for hERG channel inhibition and platelet aggregation, in vivo for cardiovascular function in dogs, and for respiratory and central nervous system functions and prostanoid metabolism in rats. No significant adverse effects of E7046 were observed in these studies except for an increase in heart rate, and a decrease of BP at 100 mg/kg of E7046 in dogs. Low risk of side effects in cardiovascular, respiratory and central nervous system is anticipated for E7046 in humans.

Preclinical safety studies thus suggest that E7046 has an acceptable safety profile in the intended population at proposed clinical doses.

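### In the first cohort the Day 14 check looks only for suspected severe immune reactions, so a DLT of another kind in Subject 1 does not space out Subjects 2 and 3

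*Protocol*

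**What the plan says.** Protocol 9.1.1.1 sets the staggered start at 125 mg.

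- **Check after Subject 1.** "If after 14 days of dosing no suspected severe immune reactions are observed, another 2 subjects (Subjects # 2 and 3) will be enrolled". If Subject 1 does have such a reaction within 14 days, "another subject (Subject #2) will be enrolled and dosed", and Subject 3 follows only if Subject 2 has none over 14 days. A reaction in both stops the cohort.
- **What counts.** "Suspected severe immune reactions (ssIR) are defined as listed in the CTCAE v4.03" class Immune System Disorders. The text names allergic reaction, anaphylaxis and cytokine release syndrome as included.
- **Where DLTs enter.** "After evaluation of the first 3 subjects for DLTs after 21 days (Cycle 1"), enrolment goes on to Subjects 4 to 6 with at most 1 DLT in 3. With more than 1, testing moves to 75 mg.
- **Dose Level -1.** Enrolment there "will follow the same staggered schema as described for Dose Level 1".
- **Spacing by day.** The limit that "no more than one subject will be dosed on the same day" is written for the cohorts after the first.

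Protocol 9.1 gives the purpose of the stagger: "to ensure exposure of a limited number of subjects in the initial dosing cohort". Protocol 9.1.1.2 requires documented agreement on DLTs before the next dose level. SAP 5.6.2 places its safety review after all subjects at a level finish Cycle 1.

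**The concern.** The check does not match the toxicities that the protocol itself anticipates. Protocol 7.1.3.3 projects gastrointestinal, testicular and cardiovascular effects, the first being "Colitis, characterized by new onset of diarrhea, which may be accompanied by abdominal pain and or gastrointestinal bleeding". None of these is named in the ssIR definition, yet a related event of Grade 3 or higher could well be a DLT.

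If Subject 1 has such a DLT by Day 14 without an ssIR, the written rule releases Subjects 2 and 3 together, and nothing in it keeps them from starting on the same day. Had the event been an ssIR, they would have started one at a time. At stake is the exposure of one further subject before the sponsor has seen how the second tolerates the drug, in a first-in-human cohort that Protocol 9.1 says calls for caution.

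**Working it through.** **The plan's own figures.** 4 cohorts x 6 = 24 in escalation; 24 + 16 = 40 at most. Both reproduce, and sequential starts change neither.

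**Tracing the rule for Subject 1 by Day 14.**

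| Event in Subject 1 | Next step as written |
|---|---|
| None | Subjects 2 and 3 both start |
| ssIR | Subject 2 alone for 14 days, then Subject 3 |
| DLT that is not an ssIR | Subjects 2 and 3 both start |

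The first and third rows lead to the same place. A DLT that is also an ssIR is caught.

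**Size.** The inputs are assumptions, because the documents give no DLT probability. Let p be the chance of a non-ssIR DLT within 14 days, equal and independent across subjects. With a constant hazard over the 21-day window, the 21-day chance is q = 1 - (1 - p)^(21/14) = 1 - (1 - p)^1.5. The alternative is sequential starts after a DLT in Subject 1, with Subject 3 not dosed if Subjects 1 and 2 both have a DLT within their 14 days.

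1. Expected subjects dosed among the first three: 3 as written; 3 - p^2 with sequential starts. At p = 0.10, 3 - 0.01 = 2.99.
2. Further subjects dosed, given a DLT in Subject 1: 2 as written; 2 - p with sequential starts.
3. Chance that Subjects 2 and 3 both have a DLT, given one in Subject 1: q^2 as written. With sequential starts it is (q - p) x q, since Subject 2's DLT must then fall on Days 15 to 21. At p = 0.10, q = 0.146, so 0.146^2 = 2.1% against (0.146 - 0.10) x 0.146 = 0.7%.
4. Unconditional chance that all three have a DLT, Subject 1's by Day 14: multiply step 3 by p. At p = 0.10, about 0.21% against 0.07%.

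| p | q | Step 1 | Step 2 | Step 3 (given a DLT in Subject 1) | Step 4 (unconditional) |
|---|---|---|---|---|---|
| 0.10 | 0.146 | 3.00 to 2.99 | 2.00 to 1.90 | 2.1% to 0.7% | 0.21% to 0.07% |
| 0.20 | 0.284 | 3.00 to 2.96 | 2.00 to 1.80 | 8.1% to 2.4% | 1.6% to 0.5% |
| 0.33 | 0.452 | 3.00 to 2.89 | 2.00 to 1.67 | 20.4% to 5.5% | 6.7% to 1.8% |
| 0.50 | 0.646 | 3.00 to 2.75 | 2.00 to 1.50 | 41.8% to 9.5% | 20.9% to 4.7% |

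The last two rows only complete the range. Protocol 9.1 and 9.2 expect moderate toxicity and possibly no MTD, and 7.1.3.3 puts 125 mg below one ninth of the human equivalent of a dog dose with only slight findings. The first rows are therefore the plausible ones at the starting dose.

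**Delay if an event occurs, without review time.** As written, Subjects 2 and 3 start on Day 15, finish Cycle 1 on Day 15 + 20 = 35, and are evaluated about Day 36. With sequential starts, Subject 3 begins on Day 15 + 14 = 29, finishes on Day 29 + 20 = 49, and is evaluated about Day 50. The difference is 14 days.

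**The case against.** The strongest reply is that the split is deliberate. Protocol 9.1 ties the caution to a novel immune therapy given to humans for the first time. The stagger then covers acute immune reactions, while DLTs have their own rule before Subjects 4 to 6. Subject 1 is dosed alone for 14 days and only three subjects are exposed before the DLT evaluation, so the stated purpose is served as written.

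The sponsor would also normally hear of the event in time. Colitis and gastrointestinal bleeding are always serious (9.5.5.2), and serious events are reported within 24 hours (9.5.8.1). Continuing a subject after a DLT, or interrupting dosing for more than 3 days, involves the medical monitor (9.4.1.1). Sections 11.1 and 11.11 allow immediate safety action or a halt. Not every bowel event would be a DLT either: 9.1.1.2 exempts an immune-related event (irAE) of Grade 3 or lower that resolves within 7 days, and counts diarrhea only if it lasts more than 3 days despite optimal care.

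Most of this stands, and it is why the point ranks low. What remains is that these provisions concern reporting, the affected subject, or discretion. None holds enrolment or makes the next two starts sequential, although the protocol already has such a rule for another class of event.

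**Conclusion.** The gap holds on the text, in a limited form: a non-ssIR DLT in Subject 1 within 14 days leaves Subjects 2 and 3 free to start together, at 125 mg and at Dose Level -1. It is a cheap improvement of the lowest tier. At the plausible values p = 0.10 and 0.20, the saving is 0.01 and 0.04 of a subject on average. The benefit lies in the unlikely case that the preclinical forecast is wrong.

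A reader might infer more than the documents support:

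- **That DLTs in the first three subjects go unheeded.** Subject 1's DLT counts toward the more-than-1-of-3 rule before Subjects 4 to 6.
- **That Subjects 2 and 3 must start together.** The text permits this but does not require it.
- **That sequential starts would remove the risk.** DLTs on Days 15 to 21 are still not caught, which is why step 3 does not fall to zero.
- **That any two events, of either kind, should stop the dose.** One ssIR plus one DLT would then end 125 mg, against the plan's tolerance of 1 DLT in 3.

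The sizes rest on assumed, equal and independent risks and a constant hazard. Figure 3 Panel B is not shown in the text available, so the finding rests on the written rule. Confidence is medium.

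**What to change.** Amend the first-cohort paragraph of Protocol 9.1.1.1 as follows.

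1. If Subject 1 has an ssIR, or an event meeting the DLT definition in 9.1.1.2, within 14 days, the investigator(s) and sponsor physician document a review before further dosing. Subject 2 is then dosed alone, and Subject 3 starts only after Subject 2's 14 days.
2. Keep the stopping thresholds. Stop before Subject 3 only if Subjects 1 and 2 both have an ssIR, as now, or both have a DLT. In the latter case the more-than-1-of-3 rule is already met and Subject 3 could not change the decision. One ssIR plus one DLT prompts a review, not an automatic stop.
3. Hold the next start for a related Grade 3 irAE that is still within its 7-day resolution window, and for no lower grade.
4. Leave the ssIR definition as it is, apply the same text to Dose Level -1, and check that Figure 3 Panel B agrees.

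The cost is one paragraph in an amendment, using the DLT review that 9.1.1.2 already describes. Nothing is delayed unless an event occurs. An event moves the three-subject evaluation by about 14 days plus review time. An irAE that begins on Day 14 and then resolves is classified by Day 14 + 7 = 21, so that hold adds at most about 7 days. Sample size is unchanged.

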**Figure 3      Schema for Dose Escalation**

### 9.1.1.2 Dose-Limiting Toxicities

Dose-limiting toxicities (DLTs) are any of the following drug related toxicities (any toxicities considered related, probably related, or possibly related to E7046) occurring during Cycle 1 as judged by the investigator.

- Nonhematologic toxicity  $\geq$  Grade 3 (except diarrhea, nausea and vomiting unless lasting  $>3$  days despite optimal supportive care)
- Confirmed (with a second measurement after 24 hours) nonhematologic appropriately-graded laboratory findings of Grade  $\geq 3$  that were  $\leq$  Grade 1 at baseline
- Hematologic toxicity:
  - Grade 4 neutropenia for  $\geq 5$  days, or Grade 3 neutropenia with fever (fever is  $38.4^{\circ}\text{C}$ ),
  - Grade 4 thrombocytopenia, or Grade 3 thrombocytopenia with bleeding or lasting  $>7$  days
- Any other toxicity assessed as related to E7046 treatment, and which in the opinion of the study investigator(s) and the sponsor physician constitutes a dose-limiting toxicity
- Subjects who have missed  $\geq 7$  days of dosing in Cycle 1 due to drug-related toxicity (but not qualifying for a DLT) will be assessed as experiencing a DLT.

Grading of toxicities is based on National Cancer Institute - Common Terminology Criteria for Adverse Events (NCI CTCAE) v4.03 ([Appendix 4](#)).

Adverse events occurring after Cycle 1 may be considered DLTs upon discussion between the investigator(s) and the sponsor physician.

The following toxicities will not be considered DLTs:

- Grade  $\leq 3$  adverse event of tumor flare (defined as local pain, irritation, or rash localized at sites of known or suspected tumor)
- Grade  $\leq 3$  immune-related adverse event (irAE) that resolves to Grade 1 or less within 7 days, while not constituting a DLT for dose escalation purposes, may preclude further administration of study drug or study drug may be continued at a reduced dose after discussion and agreement with Eisai medical monitor.
  - An irAE, a subset of AEs, is defined as a clinically significant adverse event of any organ that is associated with study drug exposure, of unknown etiology, and is consistent with an immune-mediated mechanism. Serologic, immunologic, and histologic (biopsy) data should be used to support an irAE diagnosis. Appropriate efforts should be made to rule out neoplastic, infectious, metabolic, toxin, or other etiologic causes of the irAE.

Subjects who for reasons other than drug related toxicity or a DLT, fail to complete 75% of the planned total dose in Cycle 1, (equivalent to 16 out of 21 days) will be replaced.

Assessment of DLTs will be discussed and agreed to by investigator(s) and sponsor physician prior to proceeding to the next dose level, and the decision will be documented.

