#### 9.1.3.2 Treatment Phase

**Treatment Phase** is Cycle 1 (Day 1 - 21) where evaluable subjects will be assessed for DLT.

At the end of the Treatment Phase subjects continue to the Extension Phase.

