10. Immunosuppressive doses of systemic medications, such as steroids or absorbed topical steroids (doses >7.5 to 10 mg/day prednisone or equivalent) must be discontinued at least 2 weeks before study drug administration.
11. Subjects with prior Hepatitis B or C are eligible on the condition that subjects have adequate liver function as defined by Inclusion Criterion #16 and Exclusion Criterion #5.
12. Left ventricular ejection fraction (LVEF) >50% on echocardiography or multiple gated acquisition (MUGA) scan.
13. Adequate renal function defined as serum creatinine <1.5 × ULN (or use SI units or calculated creatinine clearance  $\geq 50$  mL/min per the Cockcroft and Gault formula [[Appendix 3](#)]).
14. Adequate bone marrow function:
  - a. Absolute neutrophil count (ANC)  $\geq 1500/\text{mm}^3$  ( $\geq 1.5 \times 10^3/\mu\text{l}$ )
  - b. Platelets  $\geq 100,000/\text{mm}^3$  ( $\geq 100 \times 10^9/\text{L}$ )
  - c. Hemoglobin  $\geq 9.0 \text{ g/dL}$
15. Adequate liver function:
  - a. Total bilirubin  $\leq 1.5 \times$  upper limit of normal (ULN) except for unconjugated hyperbilirubinemia of Gilbert's syndrome.
  - b. Alkaline phosphatase, alanine aminotransferase (ALT), and aspartate aminotransferase (AST)  $\leq 3 \times$  ULN ( $\leq 5 \times$  ULN if subject has liver metastases). If alkaline phosphatase is  $>3 \times$  ULN (in absence of liver metastases) or  $>5 \times$  ULN (in presence of liver metastases) AND the subject also is known to have bone metastases, the liver-specific alkaline phosphatase must be separated from the total and used to assess the liver function instead of total alkaline phosphatase
16. Adequate blood coagulation function as evidenced by an International Normalized Ratio (INR)  $\leq 1.5$ .
17. Willing and able to comply with all aspects of the protocol.
18. Provide written informed consent prior to any study-specific screening procedures.

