**Table 6 Schedule of Procedures / Assessments in Study E7046-G000-101**

	Phase	Pretreatment a		Treatment			Extension		
		Period	Screening	Baseline	Cycle 1		Treatment Continuation b (Cycle 2 and beyond)	Off-Treatment c	Follow-up c
CRF	Visit	1	2	3	4	5	6, 8, etc.	7, 9, etc.	98
	Day	-28 to -1	-3 to -1	1	8	15	1	8 (C2-6 only)	99
Procedures/Assessments									
S	Informed consent		X						
S	Inclusion/exclusion criteria		X						
S	Medical history		X						
S	Physical examination d and Vital signs e	X	X	X	X	X	X		X
N	Echocardiogram / MUGA f	X							X
S	Pregnancy test g	X	X	X					X
S	ECOG performance status	X	X	X			X		X
S	12-lead ECGs h	X	X	X			X		X
S	ECG Holter monitoring i			X	X				
S	Hematology / Blood chemistry j	X	X	X	X	X	X	X	X
S	Urinalysis k	X		X	X	X	X	X	X
N	Genomic DNA l		X						
S	PK and PD urine collection m			X	X				
S	PK blood samples n			X	X				
N	PD blood samples o		X o	X	X o	X o	X o		X o
N	Paired tumor biopsy and archived tumor p	X					X p		
N	 FDG PET/CT q		X				X q		
S	Tumor assessments: CT or MRI r	X		Every 6 weeks or sooner if clinically indicated					
S	CT or MRI of the brain s	X		X					
N	Bone Scan t	X		Every 24 wks, or sooner if clinically indicated, and at confirmation of irCR					
S	E7046 administration u			Continuous daily dosing					
S	Adverse Events v	X	X	X					X
S	Prior and concomitant medications v	X	X	X					X
S	Survival status w								X

For CRF: S = standard assessment, N = nonstandard assessment (study-specific), N/A = not applicable.

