### 9.7.2 Determination of Sample Size

The sample size of 30 to 40 subjects is considered adequate for the purposes of selecting a dose.

The expected sample size for the dose escalation part of this trial will be up to 24 subjects. Per the dose escalation design adopted and modified from the traditional 3+3 design ([Section 9.1.1.1](#)), there will be a maximum of 4 planned cohorts and there will be 6 subjects each cohort to allow for adequate assessment of tolerability, clinical benefit, PK, PD data and integrated evaluation of safety so as to select RP2D. Additional 6 to 16 subjects will be enrolled in the expansion cohort to confirm RP2D.

The dose escalation part and the extension part yield a total maximum sample size of 40 subjects.

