5.6.2 Dose Limiting Toxicity

After all subjects in a dose level tested complete the first treatment cycle, safety information for those subjects will be reviewed by the Eisai clinical team together with the principal investigator/s and dose limiting toxicity (Yes/No) and reason(s) (see Section 13.3) for experiencing a dose limiting toxicity (DLT) as well as date and dosage of study drug when the DLT occurred will be determined for each subject. This result will be listed for the study report.

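### The nonhematologic laboratory DLT criteria contradict each other and SAP 13.3 omits one of them, so the same event can count or not where escalation turns on 1 versus 2 DLTs in 6

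*Protocol*

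**What the plan says.** Protocol 9.1.1.2 lists the DLT criteria as alternatives, so meeting any one is enough, provided the toxicity is drug-related and "occurring during Cycle 1 as judged by the investigator". Two of them bear on nonhematologic laboratory values:

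- **Criterion 1** is nonhematologic toxicity of Grade 3 or higher. Its only exception is for diarrhea, nausea and vomiting of limited duration.
- **Criterion 2** is "Confirmed (with a second measurement after 24 hours) nonhematologic appropriately-graded laboratory findings of Grade" 3 or higher, and the finding must have been Grade 1 or lower at baseline.

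The Synopsis (Study Design) carries the same pair. SAP 13.3 reproduces the list without criterion 2. SAP 5.6.2 sends the cohort review to 13.3 for the reasons for a DLT.

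On timing, Protocol 9.1.3.2 says that the Treatment Phase "is Cycle 1 (Day 1 - 21) where evaluable subjects will be assessed for DLT". In Table 6 the row "Hematology / Blood chemistry" is marked in Cycle 1 on Days 1, 8 and 15, and next on Day 1 of Cycle 2. Footnote j names a complete blood count only for Days 1 and 8. Section 9.5.5.3 has samples drawn before dosing and reviewed before drug is given at the start of each cycle. Section 9.1.1.2 adds: "Adverse events occurring after Cycle 1 may be considered DLTs upon discussion between the investigator(s) and the sponsor physician". The SAP places the review "After all subjects in a dose level tested complete the first treatment cycle".

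**The concern.** The two criteria set different conditions for one kind of event. One asks for neither confirmation nor a baseline grade; the other asks for both. Because either is sufficient, the stricter one has no effect unless the first is silently narrowed, and the text does not narrow it. The SAP then drops the stricter one, so the two documents can classify one subject differently.

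DLT incidence is what determines the MTD, a primary endpoint. Under 9.1.1.1 and 9.1.1.3 the dose goes up with 1 or fewer DLTs in 6 and escalation stops with 2 or more. In the first cohort, a count of 1 versus 2 among the first 3 subjects also decides whether enrollment continues at that dose. One reclassified subject can change either decision.

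**Working it through.** **1. The plan's own figure.** Section 9.7.2 says "The sample size of 30 to 40 subjects is considered adequate for the purposes of selecting a dose". Four cohorts of 6 give 4 × 6 = 24; adding 6 to 16 gives 30 to 40. This reproduces. The documents state no expected DLT rate and no operating characteristic for the 2-of-6 rule, so there is no stated figure against which to measure misclassification.

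**2. The criteria side by side.** Take a drug-related, nonhematologic laboratory finding in Cycle 1. In the table, 'No' means not a DLT unless the catch-all criterion (joint opinion of investigator and sponsor physician) or the missed-dosing criterion applies.

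| Event | Protocol, criterion 1 includes labs | Protocol, criterion 1 excludes labs | SAP 13.3, first criterion includes labs | SAP 13.3, first criterion excludes labs |
|---|---|---|---|---|
| A. Grade 3, not confirmed, baseline Grade 1 or lower | DLT | No | DLT | No |
| B. Grade 3, confirmed, baseline Grade 1 or lower | DLT | DLT | DLT | No |
| C. Grade 3 or 4, confirmed, baseline above Grade 1 | DLT | No | DLT | No |

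Where criterion 1 includes laboratory values, every event meeting criterion 2 already meets criterion 1. Where it excludes them, event C cannot meet criterion 2 at any grade, and SAP 13.3 has no nonhematologic laboratory criterion left. No row gives the same answer in all four columns.

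**3. Can event C arise?** Inclusion criterion 15b admits liver enzymes up to 3 × ULN, or 5 × "ULN if subject has liver metastases". Appendix 4 gives only general grade descriptions and no enzyme cut-offs. That such a subject is above Grade 1 at entry is therefore an assumption, though a plausible one.

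**4. When does one disputed subject decide the cohort?** When exactly 1 of the other 5 has a DLT. The probability is 5p(1 − p)^4, taking subjects as independent with assumed rate p:

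- p = 0.10: 5 × 0.10 × 0.90^4 = 0.328
- p = 0.20: 5 × 0.20 × 0.80^4 = 0.410
- p = 0.33: 5 × 0.33 × 0.67^4 = 0.332

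**5. Shift in the stopping probability.** P(2 or more of 6) = 1 − (1 − p)^6 − 6p(1 − p)^5. Suppose the broad reading of criterion 1 adds 5 or 10 percentage points of laboratory events (an assumption). From p = 0.10, the probability goes from 0.114 to 0.224 or 0.345. From p = 0.20, it goes from 0.345 to 0.466 or 0.580. Read backwards, these are the falls if the narrow reading is applied. If no disputed event occurs, the shift is zero.

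**6. Schedule.** With 21-day cycles and no visit windows before Cycle 3, Cycle 2 Day 1 is nominally Day 22. Leaving Day 22 aside, the doses of Days 15 to 21 (7 of 21, or 33%) have no later scheduled sample within Days 1 to 21. Counting Day 22, each dosing week is followed by one pre-dose sample. No passage says which applies.

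The hematologic criteria need durations: Grade 4 neutropenia for 5 days or more, and Grade 3 thrombocytopenia for more than 7 days. A Grade 4 count on Day 8, with lower grades on Days 1 and 15, could reflect an episode of under 1 to almost 14 days. Scheduled samples 7 days apart cannot time that by themselves.

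**The case against.** The strongest reply is that any trialist would treat the specific criterion as governing: criterion 2 covers laboratory values and criterion 1 clinical toxicity. DLT calls are also agreed and documented by investigators and sponsor physician before the next dose level, and a catch-all criterion is available. This is a sensible reading, but the text does not state it. It leaves subjects above Grade 1 at entry to discretion, and under it SAP 13.3 would have no nonhematologic laboratory criterion. The joint decision makes each call considered; it does not make the rule the same across cohorts or documents.

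A reader might infer something stronger from the schedule: that it cannot support the DLT rules and that laboratory DLTs are under-counted. The documents do not support that.

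- A DLT is dated by when it occurs, not by when it is first seen. The Day 22 sample is drawn before Cycle 2 dosing, is reviewed, and reflects Cycle 1 exposure only. Later events may also be considered DLTs.
- Off-schedule testing is implied by the 24-hour repeat, by the 72-hour exemption in Table 2 footnote d, and by follow-up of adverse events.
- After the first cohort no more than one subject is dosed per day. When the last subject finishes Day 21, the others have nominally passed Day 22.
- Read literally, the overlap between criteria 1 and 2 raises the count rather than lowering it.

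The large effect that such a reader might compute is an upper bound. With a true rate of 33% and the last third of the window lost, the observed rate is 0.33 × (1 − 1/3) = 0.22, and P(2 or more of 6) falls from 0.642 to 0.394. That needs every DLT to be a laboratory finding and every Day 22 finding to be discarded. If half are laboratory findings, the figure is 0.524. If Day 22 is counted, this loss disappears. Section 7.1.3.3 anticipates mainly intestinal, testicular and heart-rate or blood-pressure effects, which makes an all-laboratory profile unlikely.

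**Conclusion.** The contradiction between the two laboratory criteria stands, as does the omission of one of them from SAP 13.3. Both affect a rule on which a primary endpoint rests, and both can be settled in wording.

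The net direction of misclassification is undetermined: a broad reading of criterion 1 raises the count, a narrow one lowers it. No magnitude follows from the documents. The figures of 33% to 41% for a decisive event, and the shifts in stopping probability, illustrate sensitivity under assumed DLT rates and independence. They do not estimate bias.

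The handling of the Day 22 sample and the counting of durations are secondary. They are unspecified details, and they do not show that the schedule fails.

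**What to change.** **Main change.** Reconcile criteria 1 and 2 in Protocol 9.1.1.2 and the Synopsis, and carry the result word for word into SAP 13.3. The text should say which criterion governs nonhematologic laboratory findings, whether confirmation and a baseline condition apply, and how a subject enrolled above Grade 1 is classified. Which rule to adopt is for the sponsor's clinicians. SAP 13.3 also differs from 9.1.1.2 on missed dosing (more than 4 days versus 7 or more) and on replacement (17 versus 16 of 21 days), so the whole section should be checked in the same pass. SAP Sections 3 and 7 name different protocol versions, and the source version should be settled too.

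**Secondary clarification.** Reconcile the Day 1 to 21 window (9.1.1.2, 9.1.3.2), the sampling schedule (Table 6 and footnote j) and the review timing (9.1.1.1, SAP 5.6.2). It should then be clear how a finding first seen on the Cycle 2 Day 1 pre-dose sample is handled, and how the duration-based hematologic criteria are determined. Any counting convention should be settled together with repeat testing. For example, counting from the first qualifying value to the first lower grade would score a single Grade 4 count on Day 8 that had improved by Day 15 as 15 − 8 = 7 days.

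**Cost.** Wording only, since the Day 22 sample is already drawn and reviewed. At most, the cohort review waits briefly for the last subject's Day 22 result.
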